17.2 RECIST v1.1 Criteria

Definition of a measurable lesion:

- At least one lesion which can be measured in at least one dimension
- In case only a solitary lesion is present, cytology and histology are recommended
- Measurement of the largest diameter, e. g. using a chest X-ray $\geq 2\text{cm}$ or with a CT scan, MRI techniques or spiral CT $\geq 1\text{cm}$

Definition of a non-measurable lesion:

All other lesions, including small lesions (longest diameter $< 1\text{ cm}$ or pathological lymph nodes with $\geq 1\text{ cm}$ to $< 1.5\text{ cm}$ short axis) as well as truly non-measurable lesions. Lesions considered truly non-measurable include: leptomeningeal disease, ascites, pleural or pericardial effusion, inflammatory breast disease, lymphangitic involvement of skin or lung, abdominal masses/abdominal organomegaly identified by physical exam that is not measurable by reproducible imaging techniques.

General guidelines:

- During the study and follow-up, use of the same investigations and the same measuring techniques
- Measurements with pictures are preferred to clinical measurements
- Clinical measurements are to include the surfaces involved e. g. cutaneous nodes (color photo including a measuring staff)
- Lesions which are not measurable: “unclear” \rightarrow control after 1 month of further therapy
- Splitting of a lesion \rightarrow addition

Baseline of measurable and non-measurable lesions:

- Estimation of the total tumor mass
- As shortly as possible prior to therapy start ($\leq 4\text{ weeks}$)
- A maximum of 2 per organ, a maximum of 5 in all, which are defined as target lesions
- Representative of all organs
- For largest lesions: a repeat of the results has to be possible
- Sum of all of the largest diameters (this sum is the reference for objective tumor response)
- All non-measurable lesions are to be considered and during the course noted as present or absent, i. e. defined as being non target lesions

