8.2 Criteria for Measurable and Non-Measurable Lesions

Measurable lesions are lesions that can be accurately measured in at least one dimension with longest at least 10 mm with CT scan, MRI techniques or spiral CT scan.

Non-measurable lesions are all other lesions, including uni-dimensionally measurable disease and small lesions (lesions without at least one diameter ≥ 10 mm), and any of the following bone lesions, ascites, pleural effusion, cysts and abdominal masses that are not confirmed by imaging techniques.

All measurable lesions up to a maximum of 2 lesions per organ and 5 lesions in total, representative of all involved organs should be identified as target lesions and recorded and measured at baseline. Target lesions should be selected on the basis of their size (in other words the lesions with the longest diameter) and their suitability for accurate repeated measurements. A sum of the longest diameter for all target lesions will be calculated and reported as the baseline sum of the longest diameter. This will be used as reference to objectively characterize the tumor. All other lesions should be identified as non-target lesions and are not measured at baseline but presence should be noted.

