8.3 Definition of Measurable Lesion Response Using RECIST Criteria

Version 1.1

Target lesions will be measured in a dimension using the longest diameter is used. The same investigational method must be used throughout.

Complete response (CR): Disappearance of all lesions and appearance of no new lesions.

Partial response (PR): At least a 30% decrease in the sum of the longest diameter of target lesions, taking as reference the baseline sum diameters. No new lesions may occur or individual lesions progress.

Progressive disease (PD): At least a 20% increase in the total of the longest diameters of target lesions, taking as reference the smallest sum on study since the treatment started (this includes the baseline sum if that is the smallest on study) or the appearance of new lesions.

If the marker lesion disappears and the progression of a lesion or the appearance of new lesions is observed elsewhere at the same time, this is also documented as a progressive disease.

Stable disease (SD): Neither a partial nor a complete response in the absence of progression.

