8.4 Definition of Non-Measurable Lesion Response Using RECIST Criteria

Version 1.1

Any other lesions, including small lesions (longest diameter < 10 mm or pathological lymph nodes with ≥ 10 to < 15 mm short axis) as well as truly non-measurable lesion are considered non-measurable or non-target lesions. Truly non-measurable lesions include: leptomeningeal disease, ascites, pleural and pericardial effusion, inflammatory breast disease, lymphangitic involvement of skin or lung, abdominal masses / abdominal organomegaly identified by physical exam that is not measurable by reproducible imaging techniques.

Evaluation of non-target lesions:

Complete Response (CR): Disappearance of all non-target lesions

Incomplete Response/Stable Disease (SD): Persistence of one or more non-target lesion(s)

Progressive Disease (PD): Appearance of one or more new lesions and/or unequivocal progression of existing non-target lesions

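### Lymph nodes are classified by short axis but selected, summed and scored by longest diameter, which can misplace a PD date or lower a best response in individual patients with mainly nodal disease

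*Protocol*

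**What the plan says.** Short axis appears in two places. Protocol 8.4 counts among the non-measurable lesions "pathological lymph nodes with ≥ 10 to < 15 mm short axis", and Appendix 17.2 gives the same limits in centimetres. Two things follow, though neither is stated outright: a node can be a target from 15 mm short axis upwards, and 10 mm is the lowest short axis that the protocol calls pathological.

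The other size rules use the longest diameter, with no exception for nodes:

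- **Measurability (8.2).** A lesion is measurable if its longest dimension is at least 10 mm on CT or MRI.
- **Baseline sum (8.2, 17.2).** "A sum of the longest diameter for all target lesions will be calculated and reported as the baseline sum of the longest diameter". The appendix has "Sum of all of the largest diameters (this sum is the reference for objective tumor response".
- **Follow-up and PD (8.3).** "Target lesions will be measured in a dimension using the longest diameter is used". PD is "At least a 20% increase in the total of the longest diameters of target lesions, taking as reference the smallest sum on study", or a new lesion. No minimum increase in millimetres is given.
- **CR (8.3, 8.4).** For targets, "Disappearance of all lesions and appearance of no new lesions". For non-targets, "Disappearance of all non-target lesions"; "Persistence of one or more non-target lesion(s" is incomplete response or SD. The table in 8.5 turns target CR with non-target SD into PR.
- **Depth of response (10.1.2).** Based on longest diameters of the targets, or on reconstructed volume.

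Section 8.1 sends evaluators to 8.5 and 17.2. The SAP adds no nodal rule. Listing 23.1 shows a sum of sizes and Listing 23.2 one size per lesion, both in mm without naming the axis.

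**The concern.** Nodes are graded on one axis and then selected and followed on another. Three consequences are possible: two sections disagree on whether a given node can be a target; a node can trigger PD while its short axis is below any value that the protocol calls pathological; and a node that has shrunk below that value still counts as disease for CR and still contributes its full length to the sum.

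Progression by RECIST is the primary endpoint event (Protocol 10.1.1, SAP 4.12). PD is also a listed reason for stopping treatment (5.4.1) and a TFTS event (10.1.2), and CR or PR defines ORR. SAP 4.2 reports seven patients, mostly in listings, but still plans the RECIST listings, Listing 24, the response table and a Kaplan-Meier plot of PFS. At that size one reclassified patient is visible: if all seven were randomized, one patient is 1/7 = 14.3 percentage points of ORR, and more if fewer were randomized.

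**Working it through.** The plan has no figure of its own to reproduce on this point. The rules come from Protocol 8.2 to 8.5 and 17.2. The documents give no lesion data, so all node sizes below are assumptions, written long x short axis in mm. Change = 100 x (new sum − reference sum) / reference sum. The limits in 8.3 are a fall of at least 30% from baseline for PR and a rise of at least 20% from the smallest sum for PD.

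1. **Measurability.** Take a node of 14 x 11. Under 8.2 the longest dimension is 14 ≥ 10, so it is measurable. Under 8.4 and 17.2 the short axis is 11, within 10 to under 15, so it is non-measurable. Both cannot apply.

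2. **Missed response.** Two target nodes go from 26 x 16 to 20 x 8 each. Longest diameters: 52 to 40, (40 − 52)/52 = −23.1%, which is SD. Short axes: 32 to 16, −50%, beyond the 30% limit, with both nodes below 10 mm. This gap arises only when the long axes fall by less than 30%. A node going from 22 x 16 to 12 x 8 falls 45.5% on the long axis and 50% on the short axis, which meets the PR limit either way.

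3. **PD from length alone.** The same two nodes go from 20 x 8 to 24.5 x 8. Longest diameters: 40 to 49, +9 mm, 9/40 = +22.5%, which is PD. The short axes have not changed.

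4. **How much other disease removes it.** A rise of d mm reaches 20% only if the whole smallest sum is at most d/0.20. For d = 9 that is 45 mm, so more than 45 − 40 = 5 mm of other, unchanged target disease removes the PD. For d = 3 the limit is 15 mm; for d = 6 it is 30 mm. For one node going from 12 x 8 to 15 x 9, plus other unchanged target disease:

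| Other target disease (mm) | Longest diameter, 3/(12 + other) | Short axis, 1/(8 + other) |
|---|---|---|
| 0 | +25.0% (PD) | +12.5% |
| 3 | +20.0% (PD) | +9.1% |
| 5 | +17.6% | +7.7% |
| 20 | +9.4% | +3.6% |
| 60 | +4.2% | +1.5% |

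5. **CR.** A target node of 12 x 8 that is still visible has not disappeared, so CR is not met. If the sum has fallen by 30% the result is PR. A visible non-target node is SD under 8.4, and 8.5 then gives PR where the targets are CR.

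6. **Would short-axis summing suffice?** No. A nodal target going from 8.0 to 9.8 mm short axis gives 1.8/8.0 = +22.5%, still PD below 10 mm. Changing the axis also leaves the disappearance wording in 8.3 and 8.4 as it is.

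**The case against.** The strongest reply is that the sum itself is defined consistently: 8.2, 8.3 and 17.2 all use the longest diameter, and 10.1.2 allows it. Classifying nodes on one axis and summing on another is awkward but not, by itself, contradictory. That part stands. It does not cover measurability, where 8.2 and 8.4 give opposite answers for the same node. Nor does it explain why a short-axis limit decides what is pathological at entry and plays no part afterwards.

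A second reply is that PFS is defined by RECIST v1.1, so sites would apply the cited criteria and treat section 8 as a summary. But 8.1 names 17.2 as the place to look, and 17.2 contains the longest-diameter sum. If some sites followed the appendix and others the cited publication, results pooled over centres (SAP 4.9) would mix two rules.

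Three stronger readings are tempting, and the documents do not support them:

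- A reader might infer that a patient with nodal disease can never reach CR. A node that is no longer visible has disappeared and does count. Only a node that has shrunk but remains visible blocks CR.
- A reader might infer that the CR wording lowers ORR. A blocked CR usually becomes PR, and ORR counts both. ORR is at risk only through the missed-response route in step 2.
- A reader might infer a bias between arms. The rule is the same in both arms, and nothing in the documents indicates that nodal disease is unbalanced.

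It is also fair to say that the PD example is favourable to the concern: its targets are all nodal and their length grows without width. Section 8.2 asks for targets that represent all involved organs, which makes such a sum less likely.

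**Conclusion.** The point holds and is minor. As written, the protocol gives two answers on whether some nodes are measurable. It also allows PD, a blocked CR or a missed response from nodes below its own 10 mm short-axis value. The PD route needs residual target disease that is small and mainly nodal: at most 45 mm in total for the two-node example, and at most 15 mm for a 3 mm growth in length. The blocked CR usually costs only the split between CR and PR.

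This rests on assumed node sizes and on reading 10 mm as the lower pathological limit, which 8.4 and 17.2 imply but do not state. The share of patients with nodal targets is not given, so the frequency cannot be estimated. With seven patients and no significance level in the SAP (4.19), what can change is individual PFS dates and best responses.

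**What to change.** Reconcile Protocol 8.2, 8.3, 8.4, 10.1.2 and 17.2 so that nodes are handled by short axis throughout, using the limits already in 8.4 and 17.2:

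- A node is eligible as a target only at 15 mm short axis or more, and enters the sum by short axis at baseline and at every later scan.
- A node, target or non-target, below 10 mm short axis counts as disappeared for CR.
- A rise in the sum made up only of nodes still below 10 mm short axis is not PD. Without this, step 6 of the check still gives PD.
- Depth of response uses the same sum.
- All other lesions keep the longest diameter.

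Because enrolment is closed, the rule should also be written into SAP 4.12, and the axis named in Listings 23.1 and 23.2. Nodal targets should be reread from the existing CTs, and any PFS date or best response that changes should be shown beside the value as first assessed. The change concerns how the endpoint is classified; it says nothing about treatment decisions.

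The cost is protocol and SAP wording and a small rereading effort in at most seven patients.

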17.3 Common Toxicology Criteria for Adverse Events (CTCAE) v.5.0

It is recommended to follow the “Common Terminology Criteria for Adverse Events (CTCAE) Version 5.0” that can be found online at the following address:

https://ctep.cancer.gov/protocoldevelopment/electronic_applications/ctc.htm#ctc_50

17.4 ECOG / Karnofsky-Index

ECOG Grade	ECOG Status	Karnofsky Grade	Karnofsky Status
0	Fully active, able to carry on all pre-disease performance without restriction.	100	Normal, no complaints
1	Restricted in physically strenuous activity but ambulatory and able to carry out work of a light or sedentary nature (e.g. light housework, office work).	90	Able to carry on normal activities. Minor signs or symptoms of disease
1	Restricted in physically strenuous activity but ambulatory and able to carry out work of a light or sedentary nature (e.g. light housework, office work).	80	Normal activity with effort
2	Ambulatory and capable of all self-care but unable to carry out any work activities. Up and about more than 50% of waking hours.	70	Care for self. Unable to carry on normal activity or to do active work
2	Ambulatory and capable of all self-care but unable to carry out any work activities. Up and about more than 50% of waking hours.	60	Requires occasional assistance, but able to care for most of his needs
3	Capable of only limited self-care, confined to bed or chair more than 50% of waking hours.	50	Requires considerable assistance and frequent medical care
3	Capable of only limited self-care, confined to bed or chair more than 50% of waking hours.	40	Disabled. Requires special care and assistance
4	Completely disabled. Cannot carry on any self-care. Totally confined to bed or chair.	30	Severly disabled. Hospitalisation indicated though death nonimminent
4	Completely disabled. Cannot carry on any self-care. Totally confined to bed or chair.	20	Very sick. Hospitalisation necessary. Active supportive treatment necessary
4	Completely disabled. Cannot carry on any self-care. Totally confined to bed or chair.	10	Moribund
5	Dead	0	Dead

17.5 CTFG (Clinical Trial Facilitation Group) recommendation for highly effective Contraception

Birth control methods which may be considered as highly effective:

For the purpose of this guidance, methods that can achieve a failure rate of less than 1% per year when used consistently and correctly are considered as highly effective birth control methods. Such methods include:

- combined (estrogen and progestogen containing) hormonal contraception associated with inhibition of ovulation¹:
 - oral
 - intravaginal
 - transdermal
- progestogen-only hormonal contraception associated with inhibition of ovulation¹:
 - oral
 - injectable
 - implantable²
- intrauterine device (IUD)²
- intrauterine hormone-releasing system (IUS)²
- bilateral tubal occlusion²
- vasectomised partner^{2,3}
- sexual abstinence⁴

¹ Hormonal contraception may be susceptible to interaction with the investigational medicinal product, which may reduce the efficacy of the contraception method

² Contraception methods that in the context of this guidance are considered to have low user dependency.

³ Vasectomised partner is a highly effective birth control method provided that partner is the sole sexual partner of the WOCBP trial participant and that the vasectomised partner has received medical assessment of the surgical success.

⁴ Sexual abstinence is considered a highly effective method only if defined as refraining from heterosexual intercourse during the entire period of risk associated with the study treatments.

The reliability of sexual abstinence needs to be evaluated in relation to the duration of the clinical trial and the preferred and usual lifestyle of the subject.

## 1 List of Abbreviations

Abbreviation	Definition
AE	Adverse event
ALAT	Alanine aminotransferase (also GPT for glutamate pyruvate transaminase)
ASAT	Aspartate aminotransferase (also GOT for glutamate oxaloacetate transaminase)
BEAM(ing)	Beads, emulsion, amplification, and magnetics (digital PCR)
(β-)HCG	(beta) Human chorionic gonadotropin
BRAF	B-rapidly accelerated fibrosarcoma
CA 19-9	Carbohydrate antigen 19-9
CEA	Carcinoembryonic antigen
CR	Complete response
(m)CRC	(metastatic) Colorectal cancer
(e)CRF	(electronic) Case report form
CRP	C-reactive protein
CT	Computer tomography
CTCAE	Common Terminology Criteria of Adverse Events (version 5.0)
ctDNA	Circulating cell-free tumor DNA
CTFG	Clinical Trial Facilitation Group
ddPCR	Droplet Digital PCR
DNA	Deoxyribonucleic acid
DPD	Dihydropyrimidine dehydrogenase
DpR	Depth of response
DSMB	Data and Safety Monitoring Board
EC	Exclusion criterium
ECG	Electrocardiogram
ECOG	Eastern Cooperative Oncology Group
EGFR	Epidermal growth factor receptor
EOT	End of (study) treatment
(m)FOLFIRI	(modified) Folinic acid, 5-FU, and irinotecan
5-FU	Fluorouracil
GGT	Gamma-glutamyltransferase
IC	Inclusion Criterium
ICD(10)	International Statistical Classification of Diseases and Related Health Problems (10 th revision from 2010)
INR	International normalized ratio
(m)ITT	(modified) Intend-to-treat set
iv	intravenous
KRAS	Kirsten Rat Sarcoma Virus
LVEF	Left ventricular ejection fraction
mAB	Monoclonal antibodies
MedDRA	Medical Dictionary for Regulatory Activities
NCI	National Cancer Institute
NRAS	Neuroblastoma RAS viral oncogene homolog
NYHA	New York Heart Association
ORR	Overall response rate
OS	Overall survival
PCR	Polymerase chain reaction
PD	Progressive disease
PFS	Progression free survival
PI3K	Phosphatidylinositol-4,5-bisphosphate 3-kinase
PP	Per-protocol
PR	Partial response
PT	Preferred terms

PTCA	Percutaneous transluminal coronary angioplasty
(a)PTT	(activated) Partial thromboplastin time
RAS(wt)	Rat sarcoma (wild-type)
RECIST	Response Evaluation Criteria in Solid Tumors (version 1.1)
SAE	Serious adverse event
SD	Stable disease
SmPC	Summary of medicinal Product Characteristics
SOC	System organ class
SP	Safety population
TLF	Tables, listings, and figures
TFTS	Time to failure of treatment strategy
TNM	Tumor, node, and metastases (classification of malignant tumors)
UICC	Union for International Cancer Control
ULN	Upper limit of normal
VEGF	Vascular endothelial growth factor
WCRF	World Cancer Research Fund
WOCBP	Woman of childbearing potential

## 2 Introduction

### 2.1 Background

Colorectal cancer (CRC) is the third most common cancer worldwide and its therapeutic management strongly depends on the disease stage and the genetic profile of the tumor. Due to improved diagnosis and introduction of new therapies including targeting therapies with anti-epidermal growth factor receptor (EGFR) or anti-vascular endothelial growth factor (VEGF) treatments, the CRC death rates declined over the past three decades.

Differentiating between right-sided and left-sided CRC, multiple randomized studies have consistently shown that primary tumor location in the right side is associated with minor response to anti-EGFR therapy despite Rat sarcoma wild-type (RASwt) status. Hence, the treatment with EGFR antibodies in first-line therapy is recommended for left-sided primary tumors with RASwt only.

Retrospective analyses of patients with RASwt metastatic CRC (mCRC) from the phase III trials CRYSTAL and FIRE-3 show that the administration of standard first-line chemotherapy with fluorouracil, folinic acid, and irinotecan (FOLFIRI) together with the monoclonal antibody (mAB) cetuximab had a markedly better prognosis on progression free survival (PFS), overall survival (OS), and overall response rate (ORR).

### 2.2 Study design

This study is an open-label, prospective, randomized, and multicenter phase II trial that will evaluate the efficacy and safety of intermittent addition of cetuximab to a (modified) FOLFIRI-based first-line therapy to patients with RAS-mutant mCRC at diagnosis who convert to RASwt using monitoring of RAS mutation status by liquid biopsy. Maximum planned treatment duration amounts to 36 months with a total trial duration of 4.5 years.

## 3 Analysis data and patient populations

In this section the planned statistical analyses will be outlined in accordance with the study protocol and with respect to the underlying data. The statistical methods will be described in detail and the Mock-ups of the tables, listings, and figures (TLF) to be used in the statistical report will be defined.

### 3.1 Study objective

The aim of this randomized study is to evaluate whether patients with left-sides RAS-mutant mCRC at diagnosis will derive benefit from the adaption of adding cetuximab to the first-line therapy with FOLFIRI after RAS-mutation status has changed to wild-type and changing back

to FOLFIRI, as required, if RAS-mutation status has changed back to mutant, depending upon, and monitored by longitudinal ctDNA liquid biopsies.

### 3.2 Analysis populations

**Modified Intention to Treat (mITT):** All randomized patients who received at least 1 dose, complete or incomplete, of study medication.

**Safety population (SP)** = mITT population.

**Per protocol (PP) population:** All randomized patients who received study treatment according to randomization and did not have major disqualifying protocol violations, i.e., did not violate any selection criterion.

### 3.3 Patient withdrawal(s)

Patients will be encouraged to complete the study but may voluntarily withdraw from the study at any time. The investigator may also, with her/his discretion, withdraw the patient from participating in this study at any time, or the sponsor may discontinue the study. Reasons for early withdrawal from the study are documented in the electronic case report form (eCRF) as:

- Study closed/terminated,
- Patient is lost to follow-up,
- Patient died,
- Investigator's decision,
- Patient withdrew consent,
- Others such as medical advice or patient wish.

Patients withdrawn by withdrawal of informed consent, patient preference, or the investigator's decision, for reasons other than PD, will be defined as premature withdrawals.

